8 HEALTHCARE RELATED COSTS OF TREATING PATIENTS WITH VERY  
9 ELEVATED HBA1C LEVELS WITH BASAL-BOLUS INSULIN REGIMEN OR BASAL  
10 INSULIN WITH A GLP-1 AGONIST)

11  
12  
13  
14 **INVESTIGATOR-INITIATED STUDY PROPOSAL**  
15 **FUNDING PROVIDED BY NOVONORDISK A/S**

16  
17  
18 **UNIVERSAL TRIAL NUMBER (UTN)**  
19 **U1111-1145-7585**

20  
21  
22  
23  
24  
25 **Department of Internal Medicine – Division of Endocrinology and Diabetes**  
26 **UT Southwestern Medical Center**  
27 **[name]**

28  
29  
30 **Correspondence to:**  
31 **[name], MPH, MSCS**  
32 **Associate Professor**  
33 **UT Southwestern Medical Center, Division of Endocrinology**  
34 **[name]**  
35 **[contact]**  
36 **[[contact]](mailto:[contact])**  
37

38

39 **BACKGROUND AND SIGNIFICANCE:**

40 1. Achieving glycemic goals in type 2 diabetes has multiple beneficial health  
41 consequences.

42 There are over 25 million patients with diabetes in the US [1], a disease with tremendous  
43 health, social, and economic implications. Studies like UKPDS [2, 3] and Kumamoto [4,  
44 5] have established an undeniable link between hyperglycemia and micro- and even  
45 macrovascular complications. Such data serves as the background for the current  
46 glycemic targets recommended by the American Diabetes Association. Despite  
47 tremendous therapeutic advances and availability of numerous new classes of drugs in the  
48 past decade, more than a third of the population with diabetes, particularly in minority  
49 groups and those with lower level of education, still does not reach glycemic targets [6-  
50 8]. Given the large epidemic of obesity and type 2 diabetes, our efforts to curb diabetes  
51 related morbidity and mortality have a whole new meaning and huge potential impact,  
52 both on patient related outcomes as well as cost of healthcare – a very timely concern for  
53 our healthcare system[9-11].

54

55 2. Treatment guidelines for type 2 diabetes advocate insulin treatment for patients with a  
56 HbA1c>10%.

57 Treatment guidelines for diabetes have been published by ADA/EASD [12] and AACE  
58 [13], with the purpose of providing guidance to healthcare providers caring for patients  
59 with type 2 diabetes and ensure best possible outcomes. Currently metformin is well  
60 accepted as the first line therapy for patients with type 2 diabetes in addition to lifestyle  
61 changes [2, 12-14]. There is no general agreement as to what is the best way to advance  
62 treatment in those who have not achieved target HbA1c levels with monotherapy [12,  
63 13]. The current ADA and AACE guidelines both recommend an individualized approach  
64 to treatment intensification which should take into consideration cost, patient's  
65 preference, and profile of available medications [12, 13] It is generally accepted that  
66 patients with HbA1c level >10 % have a low probability of achieving ideal glycemic  
67 target of <7.0% with any of the traditional oral hypoglycemic agents, or even after basal  
68 insulin-only initiation. Therefore such patients will require prandial insulin, whether  
69 administered as a mixed formulation or basal-bolus regimen in order to archive glycemic  
70 goals [6, 12, 13, 15-26].

71

72 3. Insulin is a very effective glucose lowering agent, but it is associated with multiple  
73 side effects and shortcomings.

74 Patients with a very elevated HbA1c (>10%) are traditionally thought to have more  
75 advanced disease [2, 6] as well as glucotoxicity [27, 28], which coupled with the need to  
76 lower HbA1c by >3% to reach glycemic targets, make insulin an obvious treatment  
77 choice [15, 29]. Insulin is considered the most effective hypoglycemic agent and  
78 therefore capable of lowering HbA1c into target range regardless of baseline glycaemia  
79 [15]. Yet an insulin based treatment regimen, when implemented correctly and  
80 intensively, takes a significant toll on the patient's lifestyle by requiring a higher  
81 commitment to disease management in the form of more frequent self-monitoring,  
82 multiple daily injections, requires more frequent dose adjustments, and a greater  
83 investment in insulin-related diabetes education [30, 31]. Furthermore, insulin treatment

84 is commonly associated with two most undesirable side effects: weight gain and  
85 hypoglycemia [30, 32].

86  
87 4. Treatment-induced weight gain has a negative effect on the disease pathophysiology  
88 and fuels its progression.

89 Most patients with diabetes are overweight and obese, development of which is often the  
90 initial event in the pathophysiology of type 2 diabetes [1, 33, 34]. Using therapeutic  
91 agents that focus primarily on blood glucose control but promote further weight gain  
92 seems counterintuitive, as this further worsens insulin resistance, which in turns results in  
93 an increase in insulin requirement, thus fueling a vicious cycle which promotes disease  
94 progression [35]. A Swedish study confirmed the deleterious effects of weight gain after  
95 diabetes diagnosis, as it demonstrated that patients with newly diagnosed diabetes who  
96 gain, rather than lose or maintain weight, are at a significantly increased risk of  
97 cardiovascular death [36].

98  
99 5. Hypoglycemia is a common side effect of intensive insulin treatment and has far  
100 reaching consequences.

101 Hypoglycemia has a greatly underestimated effect on patients' life and beyond. Even  
102 seemingly minor hypoglycemic events create treatment related anxiety, heighten social  
103 anxiety, can limit or interfere with the patients' professional and social life, and can lead  
104 to treatment noncompliance. Hypoglycemia, especially severe hypoglycemia, has also  
105 been associated with untoward medical consequences like dementia, cardiovascular risk,  
106 seizures, and even death [30]. It also carries a great financial burden both in direct cost  
107 related to the event, as well as indirect costs like lost wages and work absenteeism [31].  
108 The effects of hypoglycemia reach beyond the patient, affecting the psychological, social,  
109 and financial well-being of the whole family [37].

110  
111 6. We need treatment algorithms which are patient-centric and offer the best overall  
112 benefit, rather than a glucose-centric approach.

113 With an ever increasing focus on personalized patient-centric treatment [12, 13], there is  
114 a renewed focus on patient-related outcomes, including treatment burden and quality of  
115 life. Insulin treatment requires an increased level of diabetes education, more intensive  
116 glycemic monitoring, a heightened awareness for potential side effects, a larger daily  
117 time commitment, all with potential negative effect on quality of life and treatment  
118 satisfaction [31, 37, 38]. The increase in treatment acuity related to insulin translates into  
119 higher healthcare related costs, a very timely concern for our economy [9-11, 31].

120  
121 7. GLP-1 agonist have pleiotropic effects which target the core pathophysiologic  
122 abnormalities in type 2 diabetes.

123 GLP-1 agonists have been a relatively recent addition to our diabetes treatment  
124 armamentarium. They exert many beneficiary actions, counteracting many of the basic  
125 pathophysiologic determinants of diabetes: enhance glucose stimulated insulin secretion,  
126 suppress glucagon production, promotes satiety, decreases food intake, improves insulin  
127 sensitivity, lower ectopic fat deposition (i.e. liver steatosis, visceral fat), etc. GLP-1  
128 agonists lower HbA1c by 1.5-2%, have a very low risk of hypoglycemia, and promote  
129 weight loss – all very desirable effects in patients with type 2 diabetes [35]. While this

130 treatment does require an injection, it is very easy to use, does not require continuous  
131 treatment titration, and greatly reduces the need for frequent glucose self-monitoring. All  
132 these attributes make it quite an appealing treatment alternative for patients with type 2  
133 diabetes. In the current diabetes treatment guidelines it is recommended as a second or  
134 third line agent after metformin failure.

135

136 8. The combination of basal insulin and GLP-1 agonists has been proven to be safe and  
137 very effective.

138 A meta-analysis of pooled data from across the LEAD program demonstrated that in  
139 patients with baseline HbA1c of > 9% liraglutide was better than glargine as an add on to  
140 oral hypoglycemic medications with average reduction in HbA1c of 1.9% [39]. Several  
141 other studies support equal or superior HbA1c reduction when a GLP-1 agonist is added  
142 to background therapy and compared to basal insulin, with the additional benefit of  
143 weight loss and minimal hypoglycemia [40-43]. GLP-1 agonist has also demonstrated  
144 superiority when added to maximized basal insulin therapy and metformin, when  
145 compared to prandial insulin alone [40, 44-48]. Furthermore, treatment with GLP-1  
146 agonist in combination with basal insulin was shown to have a synergistic effect on  
147 glycemic control, with GLP-1 agonists exerting an insulin sparing effect, as well as  
148 ameliorating or eliminating the undesirable weight gain associated with insulin therapy.

149

150 The current evidence suggests the combination of metformin, GLP-1 agonist, and basal  
151 insulin to be the most effective and simple strategy to achieve near normal glycemia in  
152 patients with a baseline HbA1c < 10%, while avoiding the side effects of weight gain,  
153 complexity of care, and hypoglycemia associated with insulin alone, or post-prandial  
154 hyperglycemia, weight gain, and hypoglycemia from the association of basal insulin to  
155 orals agents [40, 41, 43-48]. It is still not known whether these favorable effects extent to  
156 the more challenging group of patients with type 2 diabetes who have a baseline HbA1c  
157 >10%. Liraglutide reduces blood glucose by several mechanisms independent of insulin  
158 secretion and its superior effect on HbA1c and weight loss was found to be largely  
159 independent of diabetes duration and baseline HbA1c [39]. Treatment with GLP-1  
160 agonists has also been associated with low secondary failure rates, durable and sustained  
161 long term blood glucose control, and durability of the initial weight loss [39, 42, 49].

162

163 **Given all these distinct properties of GLP-1 agonists and simplicity of use, we**  
164 **propose they could represent a viable alternative to intensive insulinization in**  
165 **patients with very uncontrolled (HbA1c >10%) type 2 diabetes.**

166

167 The aim of this study is to compare a GLP-1 plus basal insulin treatment regimen to a  
168 basal-bolus treatment regimen in patients with very uncontrolled (HbA1c>10%) type 2  
169 diabetes. We will compare the two regimens with respect to efficacy in improving  
170 glycemic control, rate of hypoglycemia, change in weight, effect on patient quality of  
171 life, treatment burden, physician time, as well as healthcare related cost. We hypothesize  
172 that the two treatment regimens will have equal effectiveness, while the GLP-1 based  
173 regimen will be superior with respect to all other variables.

174

175 We chose to focus on a specific patient population which is generally considered to be  
176 most challenging to manage, use up greater healthcare resources, have higher potential for  
177 morbidity, and have traditionally been excluded from most clinical trials. Therefore this  
178 study will fill in an existing knowledge gap and provide high level evidence for future  
179 diabetes treatment guidelines pertaining to this patient population. We will obtain  
180 information not only in regards to the effectiveness of the treatment, but also safety and  
181 impact on healthcare cost beyond the cost of the drug.

182

183 Our findings will have great impact on the way we treat this – unfortunately – significant  
184 segment of the diabetic population, with huge potential benefits beyond just glycemic  
185 control, including quality of life, other metabolic co-morbidities, healthcare cost, etc.  
186 Additionally, if our proposed alternative regimen proves to be superior, this would  
187 represent a simple treatment alternative that primary care physicians can easily initiate  
188 and manage in their office, mitigating the need for referral to the specialist – representing  
189 a further healthcare cost control in addition to that observed in our study and a small step  
190 in alleviating the huge shortage of endocrinologists nationwide.

191

192 **We are uniquely positioned to perform this study for multiple reasons: (1) we serve**  
193 **the largest county hospital in the US where this specific study population is greatly**  
194 **overrepresented; (2) our county hospital is a closed healthcare system, where all**  
195 **actual health-care related costs incurred by these patients can be readily captured;**  
196 **(3) the PI (and sub-I) have extensive clinical experience with this study population;**  
197 **(4) the PI has extensive clinical research experience, with proven track record of**  
198 **successfully designing clinically relevant studies and caring out to final completion**  
199 **even the most challenging research protocols.**

200

201

## 202 **SPECIFIC OBJECTIVES:**

203 We plan to evaluate a new GLP-1 based treatment strategy for patients with very  
204 uncontrolled (HbA1c>10%) type 2 diabetes and compare it to a standard basal-bolus  
205 insulin regimen.

206

207 Primary Specific Aim: To determine the non-inferiority of the basal insulin-GLP-1  
208 agonist combination therapy to full basal-bolus insulin combination therapy in patients  
209 with very uncontrolled (HbA1c>10%) type 2 diabetes.

210

## 211 **Specific aims:**

- 212 1. Compare the two treatment regimens with respect to a disease and patient-  
213 relevant composite outcome of effectiveness (HbA1c <7%) and safety (no  
214 hypoglycemia and no weight gain);
- 215 2. Compare the two treatment regimens with respect to treatment burden (number of  
216 daily shots, amount of glucose self-monitoring, need for treatment titration);
- 217 3. Compare the two treatment regimens with respect to quality of life [as measured  
218 by a disease specific (DQOL) questionnaire and general health (SF-36)  
219 questionnaire];

220 4. Compare the two treatment regimens with respect to all healthcare related costs:  
221 actual cost of the pharmacologic agents, glucose monitoring supplies, all other  
222 pharmacologic (non-study related) and non-pharmacologic healthcare related  
223 costs (outpatient and inpatient, diabetes related and non-diabetes related). We will  
224 also compare actual physician time spent during office visits and non-visit related  
225 care of these patients. While no actual dollar amount can be attached to this  
226 (phone visits and longer office visits required by the need for extra patient  
227 education are not customarily reimbursable) time commitment is of great  
228 relevance to our physicians who care for these very complex patients.  
229

230 **Primary outcome:**

231 Change in HbA1c from randomization to 26 weeks of therapy.  
232

233 **Secondary outcomes:**

- 234 1. The main secondary outcome is a less traditional but very patient-centric and  
235 clinically meaningful composite outcome of HbA1c <7% AND no documented  
236 hypoglycemia (capillary glucose level <56 mg/dl) AND no significant weight  
237 gain (<3% body weight) during the 6-mo study follow-up;
- 238 2. % reaching target HbA1c of <7% at end of study;
- 239 3. 7-point glucose profile results;
- 240 4. % patients reaching pre-specified “treatment failure” outcome;
- 241 5. Change in weight from baseline (both absolute weight lost and percent of body  
242 weight);
- 243 6. % patients with weight loss >5% of body weight;
- 244 7. Number of hypoglycemic episodes defined as mild (symptoms of hypoglycemia  
245 confirmed by a CBG reading of <70 mg/dl), moderate (any CBG reading <56  
246 mg/dl), severe (need for help to recover regardless of CBG reading);
- 247 8. Number of patients experiencing any hypoglycemic episodes;
- 248 9. DQOL questionnaire score;
- 249 10. SF-36 questionnaire score;
- 250 11. Number of daily injections;
- 251 12. Total daily dose of insulin;
- 252 13. Health care cost, total;
- 253 14. Health care cost, diabetes-related;
- 254 15. Total number of CBG checks/study;
- 255 16. Number of CBG checks/month;
- 256 17. Number of titration events by healthcare professional;
- 257 18. Number of titration events by patient;
- 258 19. Healthcare provider time during scheduled office (minutes/visit);
- 259 20. Healthcare provider time, unscheduled (total minutes);
- 260 21. Compliance with pharmacologic therapy;
- 261 22. Change in LDL cholesterol from baseline;
- 262 23. Change in Triglycerides from baseline;
- 263 24. Tolerability - defined as percentage of patients with side effects (other than  
264 hypoglycemia) related to the study medications;

265 25. Tolerability - defined by percentage of patients dropping out of the study due to  
266 side effects related to the study medications.  
267  
268

[figure not shown]
269 **RESEARCH DESIGN AND METHODS**

270 **Study type:**

- 271 • Single Center (UT Southwestern Medical Center at Dallas, TX)
- 272 • Randomized
- 273 • Single blind (evaluator)
- 274 • Two treatment arms (treatment and control)
- 275 • Length of intervention: 6 months
- 276 • Efficacy & safety trial
- 277 • Non-inferiority trial for primary outcome

278  
279 **Study Design:**

280 We will conduct a prospective, randomized, single blind, two-arm, parallel trial  
281 comparing two treatment regimens (liraglutide, detemir, and metformin versus aspart,  
282 detemir, and metformin) in patients with very uncontrolled (HbA1c>10%) type 2  
283 diabetes. The investigator performing the study related measurements will be blinded to  
284 the patients' treatment assignment.

285  
286  
287 Figure 1: Study design showing the run-in period, followed by the randomization visit  
288 and the 6-mo intervention period.  
289

290 The University of Texas Southwestern Medical Center Institutional Review Board will  
291 review the study and approve all relevant documents. Furthermore, study approval will be

292 obtained from Parkland Health and Hospital System (PHHS), which represents the study  
293 site.

294

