513 All safety assessments are performed at each visit, in person or by phone. Any  
514 unanticipated or serious adverse events will be reported to the local IRB and FDA in  
515 accordance with local guidelines.

516

- 517 1. Hypoglycemia – All plasma glucose values  $\leq 70$  mg/dL, as well as values  $>70$   
518 mg/dL when hypoglycemic symptoms have occurred, should be recorded by the  
519 subjects in the blood glucose diaries provided at each visit. The recording should  
520 include:

- 521 • date of hypoglycemic episode

- 522 • time of hypoglycemic episode
- 523 • time of last main meal prior to episode
- 524 • whether the episode was symptomatic
- 525 • whether the episode was in relation to exercise
- 526 • whether seizure or coma developed
- 527 • whether the subject was able to treat him/herself
- 528 • the plasma glucose level before treating the episode

529

530 The following definitions for hypoglycemia will be used:

- 531 • Mild- Symptomatic or asymptomatic hypoglycemia with blood glucose 56-69
- 532 mg/dl and subject was able to treat him/herself
- 533 • Moderate- Symptomatic or asymptomatic hypoglycemia with blood glucose <56
- 534 mg/dl and subject was able to treat him/herself
- 535 • Severe- Blood sugar <70 mg/dl or symptoms highly suggestive of hypoglycemia
- 536 and the subject needed assistance to be treated with carbohydrates, glucagon, or
- 537 other resuscitative actions
- 538 • Nocturnal hypoglycaemia- blood glucose <70 with a time of onset between 00:01
- 539 and 05:59 (both included)
- 540 • Relative Hypoglycemia- Blood glucose >69 mg/dl with symptoms highly
- 541 suggestive of hypoglycemia
- 542 • Probable symptomatic hypoglycemia- Symptoms highly suggestive of
- 543 hypoglycemia but subject did not measure blood glucose.

544

545 2. Other treatment specific side effects

- 546 • Nausea, vomiting, diarrhea, and headache;
- 547 • Abdominal pain suspicious for pancreatitis would prompt immediate physician
- 548 evaluation and laboratory testing for amylase and lipase measurement which
- 549 would be processed immediately and analysed by PHHS Clinical Laboratory.

- 550 3. Pregnancy Test- females of childbearing potential will have urine pregnancy test
- 551 (human chorionic gonadotropin, hCG) performed if clinically indicated in the
- 552 assessment of the investigator. Urine-stick pregnancy test will be performed for
- 553 females of childbearing potential at any time during the trial, if a menstrual period is

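### The main secondary composite is failed only by a capillary glucose below 56 mg/dl, so an assisted episode without such a reading still counts as hypoglycemia-free; the hypoglycemia grades are also defined in two different ways

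*Combined protocol and SAP*

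**What the plan says.** Secondary outcomes, item 1, names the composite as the main secondary outcome. It gives the only operational rule for the hypoglycemia part: "hypoglycemia (capillary glucose level <56 mg/dl) AND no significant weight" gain, over the six-month follow-up. Specific aim 1 describes the same composite as a "relevant composite outcome of effectiveness (HbA1c <7%) and safety (no" hypoglycemia and no weight gain), without a threshold. The sample size section, which expects 25% versus 5% to reach the composite, and the secondary analyses in the Statistical Analysis Plan also give no threshold.

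Item 7 of the same list counts episodes by grade: "Number of hypoglycemic episodes defined as mild (symptoms of hypoglycemia" "confirmed by a CBG reading of <70 mg/dl), moderate (any CBG reading <56" mg/dl), and "severe (need for help to recover regardless of CBG reading"). Item 8 is "Number of patients experiencing any hypoglycemic episodes".

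Assessments for Safety, item 1, has its own list, introduced as the definitions to be applied. It includes "Mild- Symptomatic or asymptomatic hypoglycemia with blood glucose 56-69" mg/dl, self-treated, and "Severe- Blood sugar <70 mg/dl or symptoms highly suggestive of hypoglycemia" together with need for assistance. Moderate there means below 56 mg/dl and self-treated. Nocturnal, relative and probable symptomatic categories are added.

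**The concern.** Specific aim 1 presents the hypoglycemia part of the composite as its safety element, yet the rule looks only at a glucose value. Both lists of grades treat need for help as what makes an episode severe, and item 7 does so whatever the reading. A patient can therefore have the worst grade of hypoglycemia and still be scored hypoglycemia-free, and be a full responder if the HbA1c and weight criteria are met.

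This is the only secondary outcome with a power statement. Patients and treating doctors are unblinded (Blinding section), so a scoring rule settled after the data are seen would be open to challenge. The second problem is that the same diaries can give different totals for outcomes 7 and 8, depending on which list is used.

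**Working it through.** This is a check of definitions. The table applies each rule to the same diary entry.

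| Diary entry | Composite component (item 1) | Item 7 | Assessments for Safety |
|---|---|---|---|
| Assisted, 60 mg/dl | Not failed | Severe (also mild if symptomatic) | Severe |
| Assisted, no reading, highly suggestive symptoms | Not failed | Severe | Severe and probable symptomatic |
| Asymptomatic, self-treated, 62 mg/dl | Not failed | No grade | Mild |
| Symptomatic, self-treated, 50 mg/dl | Failed | Mild and moderate | Moderate |
| Assisted, 50 mg/dl | Failed | Moderate and severe (also mild if symptomatic) | Severe |

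**Rows 1 and 2** are the gap in the composite. Both lists call the episode severe, but item 1 has no criterion that it meets. The unqualified wording in aim 1, the sample size section and the analysis plan does not close the gap. Read broadly, it conflicts with item 1; read narrowly, it inherits item 1's rule.

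**Row 3** is the difference between the lists that matters most. Item 7 requires symptoms for mild and a reading below 56 mg/dl for moderate, so the episode has no grade. Under the safety list it is mild. A patient with only such episodes counts in outcome 8 under one list and not under the other.

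**Rows 4 and 5** arise because mild in item 7 has no lower glucose bound and moderate has no self-treatment condition. The patient has a qualifying episode either way, so only the per-grade counts in outcome 7 move.

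**The stated power.** The plan gives at least 80% for 25% versus 5% at two-sided alpha 0.05. With 50 per arm (100 randomized 1:1) and a mean proportion of (0.25 + 0.05)/2 = 0.15, the pooled normal approximation gives

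z = [0.20·√50 − 1.96·√(2·0.15·0.85)] / √(0.25·0.75 + 0.05·0.95) = (1.414 − 0.990)/0.485 = 0.88, so power is 0.81.

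The stated figure reproduces on that basis. At 44 completers per arm it depends on the test: 0.76 by the same formula, 0.80 by exact enumeration of the uncorrected chi-square. That is a separate matter.

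**Why no corrected figure follows.** It would need, by arm, the proportion of otherwise successful patients who had an assisted episode and no reading below 56 mg/dl. The documents do not give this. The risk sections give only broad frequency bands for hypoglycemia, with no split by assistance or by reading.

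**The case against.** The strongest reply is that item 1 makes a legitimate choice. The threshold is explicit and measurable, and a composite need not include every grade. Assisted episodes are counted in item 7, fall within item 8, and are summarised with the safety data. All of that is true. It does not remove the difficulty, because reporting an episode elsewhere does not change the composite score of a patient who needed help.

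Second, the sentence that introduces the safety definitions says they are the ones to be applied. If they govern throughout, the 62 mg/dl episode is mild and counts in outcome 8. This is a reasonable reading, but the sentence stands under the safety assessments, item 7 carries its own definitions, and neither list refers to the other.

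Third, if each episode takes its highest grade, rows 4 and 5 resolve themselves, and probable symptomatic can be seen as a mode of ascertainment, not a grade. This stands as the natural reading, but the plan does not state it.

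Fourth, the affected group is narrow: an assisted episode, no reading below 56 mg/dl in six months, HbA1c below 7% and weight gain under 3%. The diary also asks for the glucose level before treatment, so missing readings should be exceptions. This stands and limits the weight of the point.

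A reader might go further and infer that severe events will be hidden, that the composite is tilted towards liraglutide, or that the stated power is wrong. The documents support none of these. Severe episodes are reported, reclassification could occur in either arm, and no rate is given from which a changed power could be calculated.

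**Conclusion.** The point holds as one of definition. Followed literally, the main secondary outcome scores a patient with an assisted episode and no capillary reading below 56 mg/dl as hypoglycemia-free, although item 7 calls that episode severe, and so does the safety list when glucose is below 70 mg/dl or symptoms are highly suggestive. The two lists also disagree on an asymptomatic, self-treated value such as 62 mg/dl, which affects outcomes 7 and 8. The remaining overlaps touch only per-grade counts.

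The number of patients affected is probably small, and the size and direction of any effect on the arm comparison cannot be derived. The primary HbA1c comparison is unaffected. The conclusion rests on taking item 1 as the operative rule, since no other section gives one. It should be corrected because the rule misclassifies patients on a prominent endpoint and the remedy is cheap.

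**What to change.** 1. Define the hypoglycemia component as no capillary glucose below 56 mg/dl and no severe (assisted) episode, whatever the reading. Use the same wording in Specific aim 1, the sample size section and the Statistical Analysis Plan.
2. Reconcile item 7 with Assessments for Safety into one non-overlapping set of outcome definitions, including a single definition of severe. Count each episode once, at its highest grade. State that this set governs outcomes 7 and 8, and whether relative and probable symptomatic episodes count in them.

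The cost is wording only. The diary already records the reading, whether there were symptoms and whether the subject could self-treat, so no new data or visits are needed. The downside is that composite rates may fall slightly in either arm, so the 25% versus 5% assumption should be rechecked against the revised definition.
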